## 2. MRI

MR carries a risk for subjects who have pacemakers, metal pieces, aneurysm clips, or other contraindications for MR.

Magnetic resonance (MR) is a technique that uses magnetism and radio waves, not x-rays, to take pictures and measure chemicals of various parts of the body. The United States Food and Drug Administration (FDA) has set guidelines for magnet strength and exposure to radio waves, and we carefully observe those guidelines.

Subjects will be watched closely throughout the MR study. Some people may feel uncomfortable or anxious. If this happens, the subject may ask to stop the study at any time and we will take them out of the MR scanner. On rare occasions, some people might feel dizzy, get an upset stomach, have a metallic taste or feel tingling sensations or muscle twitches. These sensations usually go away quickly but we will ask subjects to tell the research staff if they have them.

There are some risks with an MR study for certain people. If subjects have a pacemaker or some metal objects inside their body, they may not be in this study because the strong magnets in the MR scanner might harm them. Another risk is the possibility of metal objects being pulled into the magnet and hitting a subject. To reduce this risk we require that all people involved with the study remove all metal from their clothing and all metal objects from their pockets. We also ask all people involved with the study to walk through a detector designed to detect metal objects. It is important to know that no metal can be brought into the magnet room at any time. Also, once subjects are in the magnet, the door to the room will be closed so that no one from outside accidentally goes near the magnet.

We want subjects to read and answer very carefully the questions on the MR Safety Questionnaire related to their personal safety. We will be sure that subjects have read the MR Safety Questionnaire and tell us any information they think might be important.

This MR study is for research purposes only and is not in any way a clinical examination. The scans performed in this study are not designed to find abnormalities. The primary investigator, the lab, the MR technologist, and the Magnetic Resonance Research Center are not qualified to interpret the MR scans and are not responsible for providing a diagnostic evaluation of the images. If a worrisome finding is seen on a subject's scan, a radiologist or another physician will be asked to review the relevant images. Based on his or her recommendation (if any), the primary investigator or consulting physician will contact the subject, inform them of the finding, and recommend that they seek medical advice as a precautionary measure. The decision for additional examination or treatment would lie solely with the subject and their physician. The investigators, the consulting physician, the Magnetic Resonance Research Center, and Yale University are not responsible for any examination or treatment that a subject receives based on

these findings. The images collected in this study are not a clinical MR exam and for that reason, they will not be made available for diagnostic purposes.

### **3. Blood Drawing and IV line Insertion**

Drawing blood and inserting an intravenous line (IV) into an arm vein are safe and standard medical procedures. Sometimes a bruise will occur at the puncture site and rarely a blood clot or infection will occur in the vein. Certain individuals may feel light-headed during venipuncture. The volume of blood collected during this study, may include screening laboratories, MRI and PET scans, will be approximately 32 tablespoons. This is not expected to have any serious negative effects on a study participant.

### **4. Nicotine Withdrawal**

Smokers that quit smoking may experience symptoms of nicotine withdrawal such as craving cigarettes, mild anxiety, restlessness, irritability, difficulty concentrating, loss of energy, and excessive hunger. These are typical symptoms that people experience when they stop smoking and they can be uncomfortable but they are not life threatening.

### **5. Risks of oral d-amphetamine**

Risks of amphetamine administration include both medical and psychiatric risks.

The frequent somatic side effects of d-amphetamine administration are cardiovascular (hypertension, palpitations, tachycardia, bradycardia, orthostasis). General effects such as sweating, feeling warm or cold, nausea, diarrhea, muscle and abdominal cramping, have been reported frequently. Behavioral effects in this dose range are increased level of alertness, talkativeness, restlessness, agitation, mood changes (usually euphoria) and anxiety. In our experience, these effects are generally transient and well tolerated. This dose of amphetamine has not been reported to induce psychotic symptoms in non-schizophrenic subjects. Infrequently blurred vision, headaches and chest tightness, and changes in EKG have been reported. There is a rare risk of permanent neurological damage and death as a result of cardiac arrest or stroke.

*Psychiatric or behavioral side effects:* General behavioral effects of amphetamine in this dose range are increased level of alertness, talkativeness, restlessness, agitation, mood changes (usually euphoria) and anxiety. In our experience, these effects are generally transient and well tolerated. This dose of amphetamine has not been reported to induce psychotic symptoms in non-schizophrenic subjects and we confirm this observation.

**10. Minimizing Risks:** Describe the manner in which the above-mentioned risks will be minimized.

**1.** The dose of radiation will be submitted for approval to the **Yale New Haven Hospital Radiation Safety Committee**. All scans will be done in the presence of medical supervision and trained staff in an institution specifically designed to support imaging studies. In the event of serious medical complications, the PET scan facilities have immediate access to or consultation with specialized medical units at the Yale-New Haven Hospital. Preparation of radiopharmaceuticals and performance of PET scans will be by radiochemists, physicians, and technologists of the Department of Diagnostic Radiology, Yale University School of Medicine.

These professionals are qualified by training and experience in the safe use and handling of radiopharmaceuticals. Subjects will be asked about their previous radiation exposure and those who have had research exposure within the past year will be excluded if their cumulative annual exposure (including the present study) exceeds FDA limits. The information on the previous radiation exposure of study subjects will be notified to the study doctor.

No PET studies will be performed on pregnant or potentially pregnant women, as confirmed by pregnancy testing during evaluation and on each scan day before initiation of any scan procedures. If subjects are breastfeeding they will not be able to participate in this research study.

**2. Minimizing risks with MRI:** All subjects will be screened for any metallic objects other MR contraindications that they may be holding or have implanted in their bodies using a questionnaire and all potential subjects with contraindications for MR will be excluded. This questionnaire will be repeated immediately before each measurement to insure that no metallic materials are brought into close proximity of the magnet, where they might be pulled toward the magnet. For additional security, subjects will be taken through a ferromagnetic metal detector immediately before going to the scan room.

**3. Minimizing risks with blood draws:** The risks of bruising, clotting, and infection will be minimized by having venipuncture performed by trained and experienced personnel using aseptic technique. To avoid injury due to fainting, the venous catheters will be inserted when the subjects are recumbent. The blood draws during PET scanning sessions will be obtained from the already inserted catheter, to minimize discomfort.

**4. Minimizing risks with nicotine withdrawal:** Subjects will meet with research staff and be counseled prior to the quit attempt to provide them with skills to help ease the withdrawal symptoms.

**5. Minimizing risks with oral d-amphetamine administration:** *Medical side effects:* Subjects will be carefully screened for absence of significant medical history and current medical conditions with a complete medical history, physical examination, routine blood tests, urine toxicology and EKG. Inclusion in the study will be limited to individuals who are between the ages of 18-55. Patients will be excluded if they have any h/o severe medical or neurological illness, any clinically significant brain abnormality, insulin dependent diabetes, a history of cardiovascular disease, or hypertension. Administration of oral d-amphetamine will take place at the PET center by a research nurse, with a physician on site. The research nurse will report vital signs to the physician prior to administering the amphetamine.

If several of the subject's blood pressure readings are recorded at  $>100$  or  $<60$  for diastolic BP or  $>160$  or  $<90$  for systolic BP while at rest, they will be evaluated by the MD. The study may be cancelled at the discretion of the MD after evaluation. Any automated blood pressure results that are abnormal will be repeated manually. The manual reading will be the official reading. Constant EKG and frequent BP monitoring will occur until the vital signs are within normal limits. If the systolic BP reaches or exceeds 200 mmHg for more than 5 minutes, an infusion of phentolamine (5 mg IV, over 10 min) or other appropriate measures may be initiated to control the blood pressure response. The study physician will be notified if those parameters are reached and he/she will supervise the treatment.

In case of chest pain, chest tightness or other symptoms suggestive of cardiac ischemia, the

experiment may be cancelled and an EKG will be obtained to rule out angina (ST segment elevation or depression as compared to the baseline EKG). Appropriate treatment will be initiated.

Upon discharge, patients will be given the phone numbers of the study physicians and will not be allowed to drive home. They will either arrange a ride or a taxi.

For Data and Safety Monitoring Plan templates, see  
<http://www.yale.edu/hrpp/forms-templates/biomedical.html>

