**General exclusion criteria:**

- Presence of acute or unstable medical or neurological illness. Subjects will be excluded from the study if they present with any history of serious medical or neurological illness or if they show signs of a major medical or neurological illness on examination or lab testing including history of seizures, head injury, brain tumor, heart, liver or kidney disease, eating disorder, diabetes.
- Presence of an Axis I diagnosis other than nicotine dependence
- Regular use of any psychotropic drugs including anxiolytics and antidepressants and other over-the-counter medications and herbal products in the past six months other than THC, per the PI's discretion. The PI will take a number of factors into consideration on a case-by-case basis including type of psychotropic drug used, frequency, and dose.
- Pregnancy/Breast feeding
- Subjects with a pacemaker or other ferromagnetic material in body.
- Subjects with a sitting pulse rate >100 bpm will be excluded
- Subjects with hypertension defined as sitting systolic blood pressure of >160 mmHg and/or sitting diastolic blood pressure of >100 mmHg will be excluded. Those individuals with hypertension that is well controlled by medication (e.g., within the above mentioned range) are not excluded
- Specifically, we will exclude subjects who have any active clinically significant deviation from the normal range in their electrocardiogram (EKG). However, subjects who have abnormalities in their EKG but the condition has been present for a while and the study cardiologist has evaluated and feels comfortable with the condition, would not be excluded on the basis of their cardiac condition. Examples of conditions that may meet these criteria (e.g., condition has been present for a while) include but are not limited to T-wave abnormalities, atrial fibrillation, prolonged PR interval, and right bundle branch block.
- Subjects with history of prior radiation exposure for research purposes within the past year such that participation in this study would place them over FDA limits for annual radiation exposure. This guideline is an effective dose of 5 rem received per year.
- Subjects with current, past or anticipated exposure to radiation in the work place
- Blood donation within eight weeks of the start of the study.

- History of a bleeding disorder or are currently taking anticoagulants (such as Coumadin, Heparin, Pradaxa, Xarelto).

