**8. How will eligibility be determined, and by whom?**

Eligibility to participate will be determined by the PI of this study after completion of the medical and psychiatric evaluation of the potential participant.

**9. Risks:** Describe the reasonably foreseeable risks, including risks to subject privacy, discomforts, or inconveniences associated with subjects' participation in the research.

Risks from this study include 1) risks associated with radiation exposure, 2) risks associated with MRI, 3) intravenous lines and blood drawing, 4) nicotine withdrawal symptoms, 5) amphetamine

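### PHNO protocol: the amphetamine safeguard excludes hypertension outright, while the eligibility list admits treated hypertension within 160/100 mmHg

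*Combined protocol and SAP*

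**What the plan says.** All references are to the [11C]PHNO protocol, the second protocol in the combined file, unless stated otherwise.

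- **Eligibility list (item 7, General exclusion criteria).** "Subjects with hypertension defined as sitting systolic blood pressure of >160 mmHg and/or sitting diastolic blood pressure of >100 mmHg will be excluded". The next sentence adds: "Those individuals with hypertension that is well controlled by medication (e.g., within the above mentioned range) are not excluded".
- **Amphetamine safeguard (item 10, Minimizing Risks, point 5).** Among the conditions for which patients are to be excluded it names "a history of cardiovascular disease, or hypertension". It gives no pressure limit, does not mention treatment or control, and does not refer back to item 7.
- **Who decides (item 8).** "Eligibility to participate will be determined by the PI of this study after completion of the medical and psychiatric evaluation". It does not say which of the two wordings applies.
- **Who is dosed (Section III, Use of Controlled Substances).** Each subject takes 0.5 mg/kg dextroamphetamine by mouth before the second scan of a set. Section 3.5 caps this at 50 mg per scan.
- **What the safeguard is for (item 9, Risks of oral d-amphetamine).** Hypertension heads the list of frequent cardiovascular effects. Death or lasting neurological harm through cardiac arrest or stroke is named as a rare risk.

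**The concern.** Item 10 tells the IRB how the cardiovascular risk of amphetamine is to be reduced, and leaving out people with hypertension is part of that answer. Staff who screen from item 7 would admit some of those people. A person with diagnosed, treated hypertension and a sitting pressure at or below 160/100 passes one section and fails the other. Two screeners could decide differently and each be following the protocol.

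What is at stake is participant safety and the accuracy of the risk description. The comparison of dopamine release between smokers and nonsmokers is not at stake.

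**Working it through.** The documents give no figure to reproduce. The check applies each rule to the same person and then asks whether anything else in the protocol settles the result.

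**Step 1. Apply both rules as written.**

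| Person at screening | Item 7 list | Item 10 safeguard |
|---|---|---|
| Sitting pressure above 160 and/or 100, treated or not | Excluded | Excluded |
| Hypertension on medication, at or below 160/100 | Not excluded, expressly | Excluded |
| No hypertension, at or below 160/100 | Not excluded | Not excluded |

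The rules disagree in the second row. The inclusion criteria in item 7 do not help, because they bar only cardiovascular conditions that are currently uncontrolled.

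**Step 2. Could item 10 be a stricter rule for a subset?** No. All subjects in this protocol are to be dosed, so the people covered by item 10 are the people covered by item 7. The age limits show this: both items say 18 to 55.

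**Step 3. Does the scan-day check settle it?** Item 10 sends a subject for physician evaluation if several resting readings are above 160 systolic or 100 diastolic (or below 90 or 60). The gap between these upper limits and those in item 7 is 160 − 160 = 0 and 100 − 100 = 0 mmHg. A treated subject who stays within 160/100 therefore meets neither the item 7 limit nor the upper scan-day limit. Above the limit the consequence is discretionary: "The study may be cancelled at the discretion of the MD after evaluation". The check acts on readings and does not address a diagnosis.

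**Step 4. Size.**

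- Planned participants: 50 smokers + 40 nonsmokers = 90 (section 3.1; item 5, Subject Population). With 50 nonsmokers (Statement of Purpose, Aim 1) it is 50 + 50 = 100, which matches the target in Section IV.
- Exposure per affected person, at one dose per two-scan set and before any repeat for scan failure: one planned dose for a nonsmoker, and one or two for a smoker depending on the optional second set.
- Number affected: not derivable. The documents give neither the number screened nor how many applicants have treated hypertension.

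**The case against.** The best defence is that item 10 takes its meaning from item 7. Item 7 answers the form's question about eligibility criteria, and item 8, on who decides, follows at once. Item 10 answers a different question, about minimizing risk. On that view item 7 governs and item 10 summarises it, with hypertension carrying the 160/100 definition. The matching scan-day limits support this.

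Item 10 also reads like carried-over text. It names only insulin-dependent diabetes, whereas the item 7 list runs to "heart, liver or kidney disease, eating disorder, diabetes" without that limit. A near-identical paragraph stands in the NCFHEB protocol, where its 18 to 55 age range does not match that protocol's general 18 to 60.

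This is a reasonable guess at intent, and it counts against assuming that item 10 was deliberately stricter. It does not remove the mismatch. Item 10 does not cite the definition, and item 7 itself calls the controlled patients individuals with hypertension, so it uses the word more widely than its own definition. If item 7 does govern, item 10 still misstates who will be dosed.

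A reader might infer two stronger points that the documents do not support:

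- **That atrial fibrillation is a second clear contradiction.** Item 7 says that people with long-standing EKG findings accepted by the study cardiologist "would not be excluded on the basis of their cardiac condition", and its examples are "T-wave abnormalities, atrial fibrillation, prolonged PR interval, and right bundle branch block". But item 10 does not define cardiovascular disease, and item 7 separately excludes heart disease and current anticoagulant use. The wording is untidy, but it is not a plain conflict.
- **That nothing else protects a treated subject.** The investigator decides after a medical evaluation, and a cardiologist reads the EKGs (section 3.4a). A physician is on site and receives vital signs before dosing (item 10). EKG and blood pressure are monitored until vital signs are normal, and discharge waits for that (section 3.5). These lower the risk, but they do not say who may be enrolled.

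**Conclusion.** The point holds for treated hypertension. For a subject on medication at or below 160/100 mmHg, item 7 does not exclude and item 10, read literally, does. No sentence reconciles them. Because every subject is to be dosed and the exclusion is offered as protection against a stated risk of death, it should be fixed.

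The conclusion assumes that hypertension in item 10 has its ordinary meaning. If it silently carries the item 7 definition, the contradiction in intent goes away but the safeguard still needs rewording.

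The 90 to 100 planned participants should not be read as the number affected or the number screened. The number affected is unknown and may be zero. No harm is shown, and no sample size, power figure or analysis depends on this.

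**What to change.** State one rule, in the same words, in items 7 and 10.

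**Safer version, which the documents do not compel.** Replace the hypertension bullet in item 7 with: *a diagnosis of hypertension, current drug treatment for hypertension, or sitting blood pressure above 160 mmHg systolic and/or 100 mmHg diastolic, is excluded.* Delete the exception for controlled hypertension, and use the same sentence in item 10. Deleting the exception alone is not enough: the 160/100 definition would remain, and a treated subject in range would still pass item 7.

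**Alternative.** If the investigator and IRB deliberately want to dose treated subjects, leave item 7 as it is. Amend item 10 to say that hypertension has the item 7 meaning and that medication-controlled hypertension within 160/100 may be dosed.

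The heart-disease and cardiovascular-disease wording in the two items could be aligned in the same amendment.

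**Cost.** A wording amendment to two sections, or to one under the alternative. The stricter rule may mean replacing a few subjects; the documents give no number. The alternative loses nobody but leaves a weaker, accurate safeguard. Target enrolment and analysis stay the same either way.

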## **PET**

PET scans may be performed on the High Resolution Research Tomograph (HRRT, 2-3 mm resolution) or another similar camera. Venous catheters will be used for i.v. administration of the radiotracers, venous blood sampling of activity, and for venous blood sampling of amphetamine plasma levels and hormone levels. At the beginning of scan, the subject's head will be immobilized and a transmission scan will be obtained for attenuation correction. PET scans will be acquired using bolus or bolus to infusion administration of up to 10 mCi of [C]PHNO and subjects will be scanned for up to 2 hours. Dynamic images of radioactivity concentration are reconstructed with corrections for attenuation, normalization, random events, scatter, and deadtime. Subject motion is corrected automatically on an event-by-event basis with the Vicra motion tracking system. Vital signs (blood pressure, pulse and respiration) are collected prior to and during each PET scan. Urine pregnancy test will be again administered on the PET scan day prior to the initiation of any imaging procedures. Smoking abstinence, when appropriate, will also be confirmed for smoking subjects prior to PET scanning.

PET scanning will then proceed as following for each aim:

Aim 1. Smoking subjects will be asked to come in for two [C]PHNO scans with amphetamine administration. The first scan will be during the first 2 weeks of withdrawal with the option to come back again at 2-8 weeks of withdrawal. Nonsmoking subjects will be asked to come in for one set of two [C]PHNO scans with amphetamine administration. Up to 10 mCi of PHNO will be administered per scan. After the first scan, subjects will take amphetamine (0.5mg/kg) by mouth, and then will be imaged again with PHNO. If technical difficulties arise, the second PET scan of the set may have to be re-scheduled and will be scheduled as soon as possible. In that case, subjects may be asked to re-take amphetamine on the day of the rescheduled PHNO scan, approximately 3 hrs prior to the scan. Amphetamine dose will not exceed 50mg per scan. Subjects will not be allowed to drive home.

In the rare event that a scan would fail post injection, subjects may repeat each scan set up to a total of 8 PHNO scans for smokers and 4 PHNO scans for nonsmokers.

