### 6. Use of Controlled Substances:

Will this research project involve the use of controlled substances in human subjects?

Yes  No *See HIC Application Instructions to view controlled substance listings.*

If yes, is the use of the controlled substance considered:

Therapeutic: The use of the controlled substance, within the context of the research, has the potential to benefit the research participant.

Non-Therapeutic: *Note, the use of a controlled substance in a non-therapeutic research study involving human subjects may require that the investigator obtain a Laboratory Research License. Examples include controlled substances used for basic imaging, observation or biochemical studies or other non-therapeutic purposes. See Instructions for further information.*

Dextro-amphetamine (0.5 mg/kg) will be given by mouth to each subject 3 hours prior to the second [C]PHNO PET scan.

7. **Continuation of Drug Therapy After Study Closure**  **Not applicable to this project**

Are subjects provided the opportunity to continue to receive the study drug(s) after the study has ended?

Yes If yes, describe the conditions under which continued access to study drug(s) may apply as well as conditions for termination of such access.

No If no, explain why this is acceptable.

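### PHNO protocol: the EKG exception in the exclusion list can admit a subject with longstanding atrial fibrillation whom the amphetamine safeguard excludes

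*Combined protocol and SAP*

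**What the plan says.** All references are to the PHNO protocol, the second of the two protocols in the combined document.

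- **Who is dosed.** Under PET in section 3.5, after the first scan "subjects will take amphetamine (0.5mg/kg) by mouth, and then will be imaged again with PHNO". Use of Controlled Substances (Section III, item 6) says that dextroamphetamine "will be given by mouth to each subject 3 hours prior to the second" PHNO scan. Smokers and nonsmokers are both covered. The dose is 0.5 mg/kg, capped at 50 mg per scan.
- **The safeguard.** Minimizing Risks (Section II, item 10, number 5) lists the patients to be excluded because of amphetamine. The list ends, and the dosing instruction begins, with "a history of cardiovascular disease, or hypertension. Administration of oral d-amphetamine will take place at the PET center by a research nurse". No exception is given.
- **The general illness exclusion.** The first bullet of the General exclusion criteria (Section II, item 7) excludes serious medical or neurological illness, "including history of seizures, head injury, brain tumor, heart, liver or kidney disease, eating disorder, diabetes".
- **The EKG exception.** The EKG bullet in the same list excludes active, clinically significant deviations. It then says that a subject whose abnormality has been present for some time, where "the study cardiologist has evaluated and feels comfortable with the condition, would not be excluded on the basis of their cardiac condition". Its examples "include but are not limited to T-wave abnormalities, atrial fibrillation, prolonged PR interval, and right bundle branch block".
- **Hypertension.** The same list defines hypertension as a sitting pressure above 160 systolic and/or above 100 diastolic, and adds: "Those individuals with hypertension that is well controlled by medication (e.g., within the above mentioned range) are not excluded".
- **Who decides.** "Eligibility to participate will be determined by the PI of this study after completion of the medical and psychiatric evaluation".

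**The concern.** The safeguard and the EKG bullet give different answers for one kind of subject. Read alone, the safeguard keeps out anyone with a history of cardiovascular disease. Read alone, the EKG bullet says that an accepted longstanding atrial fibrillation is no ground for exclusion. Nothing in the protocol says which text governs, and the investigator who settles eligibility has both.

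This matters because of the drug. The section on risks of oral d-amphetamine lists raised blood pressure, palpitations, and fast or slow heart rate among the frequent effects. It also states a rare risk of death or lasting neurological injury through cardiac arrest or stroke. The exclusion of cardiovascular history is there to keep the subjects most exposed to those effects away from the drug. An example in the eligibility list that names an arrhythmia as acceptable works against it.

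**Working it through.** No arithmetic applies: the point depends on no alpha, effect size, standard deviation or sample size. The check is to set the texts side by side and trace one subject through them.

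**1. Can a subject enrol and avoid amphetamine?** No. Both the PET section and Use of Controlled Substances give it to each subject. The EKG exception can therefore only admit people who will be dosed.

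**2. Trace a subject** aged 18-55 with longstanding atrial fibrillation, controlled, with a sitting pulse not above 100, off anticoagulants, and accepted by the study cardiologist.

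| Rule | Result |
|---|---|
| Age 18-55 (inclusion list and safeguard) | Passes |
| No current uncontrolled cardiovascular condition (inclusion) | Passes, if controlled |
| Pulse above 100 (exclusion) | Passes |
| Current anticoagulant use (exclusion) | Passes |
| History of serious illness, heart disease named (first exclusion bullet) | Excluded, if atrial fibrillation counts as heart disease |
| EKG bullet | Not excluded; atrial fibrillation is a named example |
| Amphetamine safeguard: history of cardiovascular disease | Excluded, no exception |

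The EKG bullet itself calls such a finding a cardiac condition, so it is hard to argue that atrial fibrillation falls outside the other two rules. The answer depends on which text is followed.

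**3. Do the other EKG examples raise the same conflict?** Not necessarily. T-wave changes, a prolonged PR interval and right bundle branch block need not amount to a history of cardiovascular disease. The exception can stand for these without contradicting the safeguard.

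**4. Is hypertension a second conflict?** The exclusion list defines the term and states that controlled cases may enter. The safeguard uses the word without a definition. If it carries the list's definition, the two agree. The paragraph that follows in the safeguard uses the same upper limits, 160 systolic and 100 diastolic, as the trigger for physician evaluation, which fits a shared threshold. A consistent reading exists; what is missing is the cross-reference.

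**5. Compare the other protocol in the file.** The NCFHEB protocol has essentially the same EKG and hypertension bullets, but there amphetamine belongs to one aim, now closed. Its safeguard could act as a stricter layer for that aim: its age range is 18-55, against 18-60 in the general list. In the PHNO protocol the age ranges agree, but the cardiac wording does not.

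**The case against.** The strongest reply is that exclusions are cumulative. The safeguard is worded for the whole study, so a subject barred by it, or by the heart-disease bullet, stays barred whatever the EKG bullet says. Dosing everyone does not by itself defeat this, since two exclusions can bind the same people. The EKG exception is also discretionary: atrial fibrillation is something that may qualify, and only if longstanding and accepted. The cardiologist is the study's own and can be expected to know that every subject takes amphetamine. Further protection comes from the exclusion of active, clinically significant EKG deviations, vital signs reported to a physician before dosing, a physician on site, EKG and blood-pressure monitoring, the evaluation and cancellation rule for resting blood pressure, the chest-pain rule, the phentolamine provision and the 50 mg cap.

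Much of this stands, and it limits both the likelihood and the harm of a wrong admission. It does not remove the conflict. The EKG bullet says affirmatively that such a subject would not be excluded on cardiac grounds, which reads as an override rather than one more exclusion. No sentence gives the safeguard precedence. Acceptance is expressed as comfort with the condition, with no mention of the drug. Monitoring acts after the eligibility decision.

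A reader might go further and infer that treated hypertension is a second contradiction that must be closed by excluding it. The documents do not support that: the list is explicit, and the safeguard can be read with its definition.

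**Conclusion.** The point holds for atrial fibrillation. Followed as written, the EKG bullet could admit a subject whom the amphetamine safeguard excludes, and that subject would be dosed. The conclusion assumes that atrial fibrillation is part of a history of cardiovascular disease, and that a screener may apply the EKG bullet without giving the safeguard precedence.

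Its reach is narrow. Because all subjects are dosed, a reader might infer that the inconsistency touches every enrolled subject. It does not: it touches only those with longstanding atrial fibrillation who meet the age, pulse and anticoagulant limits and whom the cardiologist accepts. That group is likely small, and the documents give no figure from which to estimate it. Nor do they show that any such person has been enrolled or dosed.

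This is a subject-safety inconsistency in eligibility that is worth correcting. It leaves the endpoint, analysis, power and sample size as they are.

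**What to change.** Amend the PHNO protocol in two places.

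1. **General exclusion criteria, EKG bullet.** Delete atrial fibrillation from the examples. Add wording such as: *This exception does not override the exclusion of subjects with a history of cardiovascular disease, including atrial fibrillation. Other longstanding EKG findings may be accepted only if the study cardiologist clears the subject for oral d-amphetamine up to 50 mg.*
2. **Minimizing Risks, number 5.** After the word hypertension, refer to the definition in the General exclusion criteria (sitting systolic above 160 and/or diastolic above 100 mmHg), so that controlled cases are treated alike in both places.

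The cost is one text amendment, a more specific statement from the cardiologist for the subjects concerned, and marginally narrower eligibility.
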